Study Title: A Comparison of the Muscle Protein Synthetic Response to Single Bolus

or Split Feeding Following Whole-Body Resistance Exercise

Principal Investigator: [name]

Co-investigators: [name], [name], [name]

Institution: Department of Kinesiology, McMaster University, Hamilton,

Ontario, [name], Canada

1 Study Purpose and Rationale:

Skeletal muscle plays crucial roles in locomotion and metabolism. Muscle protein turnover – protein synthesis and breakdown – governs phenotypic adaptations to loading (i.e. hypertrophy and atrophy). The difference between rates of muscle protein synthesis (MPS) and muscle protein breakdown (MPB) determines net protein balance, such that skeletal muscle is in a net anabolic (MPS>MPB), catabolic (MPS<MPB) or stable (MPS=MPB) state [1]. Resistance exercise training (RET) is a potent anabolic stimulus that increases MPS, the effect of which is enhanced when RET is combined with protein consumption [2].

In young, healthy individuals, it has been widely accepted that a protein dose of ~20-25 g (~0.25-0.30 g protein/kg body mass) maximally stimulates MPS following RET. and higher doses result in irreversible amino acid oxidation [3]. Several studies have obtained similar results, showing increased amino acid oxidation and urea production when larger doses of protein that cannot be fully utilized for MPS are consumed [4, 5]. Following full-body RET as opposed to only lower-limb RET, a slightly larger dose of protein (40 g) may be more effective at stimulating MPS (compared to 20 g) [6]. Despite the literature suggesting an upper limit of ~20-25 g of protein/meal following RET, a recent study concluded that the ingestion of 100 g of protein at a single meal (so-called onemeal a day - "OMAD" - style feeding) provides a larger and more sustained MPS response compared to 25 g of protein [7]. These findings challenge the notion that protein meal distribution is important in the post-exercise MPS response [8, 9]. However, we propose that a per meal paradigm is correct and that even 100g OMAD is not as effective as 3 evenly distributed meals. Therefore, the purpose of this study is to compare the MPS response between a single high-dose protein bolus and a split feeding (3 meals per day) protocol following RET in both male and female participants.

2 Description of the Population

Inclusion Criteria:

- English-speaking
- Male or Female, aged 18-30 years
- Healthy, non-smoking/vaping
- BMI between 20 and 30 kg/m²
- Not taking any medication or with any medical condition that, in the opinion of the investigators, would compromise the study outcome or the safety of the research participant. For example, taking any corticosteroids or antibiotics and individuals with any metabolic disorders like diabetes.
- No contraindications to proteins provided whey, pea, soy, egg in meals
- Ability to provide informed consent

Exclusion Criteria:

- Subject has any concurrent medical, orthopedic, or psychiatric requirements that, in the opinion of the investigators, would compromise their ability to comply with the study requirements
- Allergy or sensitivity to study ingredients
- Individuals who are incompetent and/or who are unable to give informed consent
- Any other condition that, in the opinion of the investigators, may adversely affect the subject's ability to complete the study or its measures or may pose a significant risk to the subject
- Any cancer, or related condition, or any genetic muscle diseases or disorders
- Current gastrointestinal disorder that could interfere with the study (e.g., IBS/IBD, diarrhea, acid reflux disease, dysphagia, etc.)
- Excessive alcohol consumption (>21 units/week) and/or a smoker (cigarettes or vaping)
- Use of corticosteroids, antibiotics, any anabolic steroid, creatine, whey protein supplements, casein, branched-chain amino acids (BCAAs) or any other natural health product (NHP), medication or supplement used for muscle strengthening/building within 45 days prior to screening
- Personal or family history of a clotting disorder or deep vein thrombosis

Recruitment Strategy

Participants will be recruited via self-referral through public advertisements (posters) at McMaster University campus, and additional advertisements will be displayed on social media and at local grocery stores/restaurants.

[figure not shown]
Sample Size

A power analysis was performed using G*Power (version 3.1.9.6). Based on previous dose-response trials (including from our facility) measuring muscle protein synthesis, we assumed a moderate effect size (F = 0.25, equivalent to Cohen's d = 0.50) [3-7]. For the present investigation, we determined 11 participants per group (22 total participants) would be sufficient to attain 80% power and an alpha at 0.05. To account for potential subject dropout, sex balancing, and missed samples, 24 participants will be recruited (12 per group).

3 Design and Detailed Description of Methodology

Trial Overview: Twenty-four healthy young men and women (age: 18-30 years; BMI: 20-30kg/m²) will be randomized using computer-generated random numbers to either a single bolus (one meal with 1.6 g/kg protein) or a split bolus group (three meals spread across the day, each with 0.53 g/kg protein). Participants will undergo D₂O heavy water ingestion, stable isotope infusion, venous blood draws, breath samples, and skeletal muscle biopsies of the *vastus lateralis*. Primary endpoints, muscle protein synthesis

(MPS), and plasma amino acid concentration will be measured throughout the day. The entire trial duration will take place over 72 hours. A schematic of the trial is provided below.

A schematic outlining the experimental design for the present study. DXA: Dual-energy X-ray absorptiometry, D₂O: Deuterated water.

Procedure Overview

This study involves the following procedures: (i) venous blood sampling via venipuncture to assess tracer, amino acid, insulin, and glucose concentrations, (ii) skeletal muscle biopsy to assess tracer incorporation (myofibrillar and sarcoplasmic fractional synthesis rates), (iii) breath samples to assess amino acid oxidation, (iv) dual-energy X-ray absorptiometry (DXA) scan to assess body composition, (v) deuterated water (D₂O) and saliva sampling to assess the incorporation of the tracer in the body water pool, (vi) gastrointestinal distress questionnaires, (vii) one repetition maximum (1-RM) on leg press, leg extension, chest press, and lat pulldown to familiarize the participant with the trial exercise, (viii) whole-body resistance exercise bout, performing 3 sets of 8-12 repetitions at 70-80% of their pre-determined one-repetition maximum, of the leg press, leg extension, chest press, and lat pulldown to increase protein sensitization.

Feeding

On the day of the infusion, participants will consume a high-protein beverage and cookies in either a single bolus or three evenly split doses (meals). Participants will consume a total of 1.6g/kg of protein, 2.5g/kg of carbohydrate, and 0.5g/kg of fat. The protein beverage will be composed of milk protein (50%), pea protein (15%), soy protein (15%)

egg protein (20%), and maltodextrin to resemble a complete meal. The cookies will provide the remaining carbohydrates and fat to fulfill the participants' daily recommended intake.

Pre-Study Assessment

The purpose and experimental design of the study will be delivered via phone or email conversations, and all questions participants may have will be addressed.

Visit 1 (1 week prior to visit 2) Consent, Screening, DXA, 1 Repetition Maximum Testing: Participants will come to McMaster University to meet with one of the researchers who will explain the study protocol. Upon the provision of written informed consent, the researcher will confirm the participant's eligibility through a review of the inclusion/exclusion criteria and medical history and participants will have their height, weight, heart rate, and blood pressure measured. Participants will then undergo a DXA scan to assess body composition. Participants will then provide a venous blood sample for laboratory testing and undergo 1-repetition maximum (1RM) testing on leg press, leg extension, chest press, and lat pulldown exercises. Participants will make a list of all the types and quantities of food they eat for 3 days during this week (3-day food diary), and before leaving the laboratory, participants will be outfitted with an accelerometer to monitor their physical activity for three days before their next visit. This visit will take ~2.5 hours.

Visit 2 (24 hours prior to visit 3) - D₂O Loading: Participants will report to the laboratory following an overnight fast at ~0700 and will provide a saliva sample and undergo the D₂O loading protocol. The D₂O loading protocol involves drinking 350 mL of D₂O (diluted with water, split up into 8 equal servings, taken every 90 minutes. The participants will be sent home with the last 5 doses (i.e. #4, 5, 6,7,8) of D₂O and will be instructed to consume them on the 90-minute schedule until complete. Participants will be asked to bring their empty D₂O bottles to their next visit. This visit will take ~5 hours.

Visit 3 (0430 – 2200) - Tracer Infusion, Blood Draws, Muscle Biopsies, Exercise, Feeding: Participants will report to the laboratory following an overnight fast at 0430 and undergo a baseline breath sample, muscle biopsy, blood sample, and urine sample. In this visit, participants will undertake a whole-body resistance exercise session, muscle biopsies, stable isotope-labelled amino acid infusion, serial breath sampling, and serial blood sampling for aminoacidemia profiling in response to feeding. Following the baseline measures, a catheter will be inserted into an antecubital vein on each arm for blood sampling and infusions, and participants will then complete a full-body resistance training session consisting of leg press, leg extension, chest press, and lat pulldown. Immediately following resistance training, participants will consume a high-protein beverage with cookies, as described earlier. Subsequent meals, if in the 3-meal group, will be consumed at 1230h and 1700h. Following the first biopsy, blood and breath samples will be taken

every 30 minutes until the first postprandial biopsy (1200). Following this biopsy, blood and breath samples will be taken every 30 minutes for the first 3 hours after each subsequent meal in the 3-meal group. In the single bolus group, blood and breath samples will be taken every hour after the first postprandial biopsy. The third and fourth biopsies will be taken at 1630 and 2200, respectively. Saliva sampling will be time-matched to the muscle biopsies. At 0500 and 1700, participants will be asked to provide a spot urine sample. Following the fourth biopsy, the catheter will be removed, concluding the visit. This visit will take ~17 hours.

Visit 4 (24 hours post visit 3) - Muscle Biopsy: 24 hours following the first biopsy in visit 3, participants will report to the laboratory following an overnight fast. During this visit, participants will undergo a final biopsy and provide a blood,breath, and urine sample. In addition, a final gastrointestinal distress questionnaire and appetite questionnaire will be completed. This visit will take around ~1 hour.

4 Definition of End-Point Measures

Primary:

Muscle protein synthesis rates

Secondary:

- Plasma amino acid concentrations
- Plasma amino acid enrichment
- Histological analysis of proteins of interest
- Amino acid oxidation

5 Hypotheses

Primary

There will be no difference in MPS between the two feeding regimes

Secondary

• There will be no significant sex-based differences.

6 Measurements and Analytical Instruments

Anthropometrics, Body Composition: Body height (m) and mass (kg) will be measured with a stadiometer and scale, respectively, to calculate BMI (kg/m2). Body composition (i.e. fat (%), appendicular lean mass (kg), and lean body mass (kg)) will be determined by dual-energy x-ray absorptiometry (DXA).

Skeletal Muscle Biopsies and Analysis: During the study, five skeletal muscle biopsies of the vastus lateralis will be collected using the suction-modified Bergström needle technique. The procedure involves the removal of a small piece of skeletal muscle tissue using a sterile, hollow needle under local anesthetic (lidocaine). A small piece of the muscle, approximately 100 mg, will be collected at each time point. After each biopsy,

incisions will be closed with an instant medical adhesive and steri-strips, and covered with a sterile bandage. Integrated rates of MPS will be determined using the D₂O method. Amino acid enrichment will be determined using isotope ratio mass spectrometry, and myofibrillar fractional synthetic rate will be determined.

Plasma amino acids, glucose and insulin: Plasma amino acid concentrations will be analyzed via gas-chromatography-mass spectrometry. Serum glucose and insulin will be assessed using fluorimetric methods as per the manufacturer's instructions.

Deuterated water: Deuterium is an isotope of hydrogen, and small amounts of deuterium are present in normal water consumed daily (~0.02%). Based on the quantities ingested during this study, the consumption of deuterium poses no health risk to the participants. 20-30 days after the participant stops drinking this water, the body water will return to its normal concentration. During the study, participants will be required to drink 350 ml of deuterated water (D₂O), split into eight equal servings.

Saliva Sampling: Saliva samples will be collected during visit 2, immediately before D₂O ingestion, in order to determine deuterium enrichments in the body water and protein-bound (albumin) pool, respectively. Participants will provide saliva samples prior to each D₂O dose (8 saliva samples on visit 2). This can be done at the lab and home. Saliva will be collected using a salivette (i.e., chewing on a piece of cotton). Saliva samples will also be collected on visit 3 and visit 4, time-matched to the muscle biopsies.

Stable isotope-labelled amino acid infusion: During visit 3, catheters will be placed on both arms or hands to collect blood samples and inject amino acid solutions throughout the day. After collecting the first blood sample, an infusion of the amino acids will be started. The amino acids will be dissolved in saline. The infusion will last for 17h. The components of the infusion will be $[1-^{13}C]$ -Leu, $[D_5]$ -Phe, and $[H_2]$ -Tyr. Details of the amino acids ingested are described in Figure 3.

[figure not shown]

Figure 3. Schematic Representation of Stable Isotope-labelled Amino Acid Infusion. RET: Resistance exercise training.

Blood collection: Blood samples will be collected at 33 (split bolus) and 28 (single bolus) time points during the trials. Split bolus: starting at 0500, and a blood draw every 30 minutes until 1530, then every 30 minutes from 1630 to 2000. Two blood draws will follow at 2200 and +24 hrs. Single bolus: Blood draw every 30 minutes from 0500 to 1300, then one draw every hour from 1400 to 2200. Finally, one blood draw at +24 hrs. Blood draws will be performed using a central venous catheter, performed by a trained and experienced study investigator. The catheter will be placed in an antecubital vein. Approximately 6 mL will be collected for each sample. The split-bolus group will have a total of 198 mL of blood collected, and the single-bolus group will have a total of 168 mL of blood collected. Samples will be used to measure plasma amino acids, glucose and insulin.

Breath Sampling: Breath samples will be collected at the same time points of the blood draws. Samples will be collected into sterile 10mL vacutainers and stored at room temperature before the analysis of ¹³CO₂ enrichment by isotope ratio mass spectrometry. CO₂ volume will be collected at baseline and each hour after the first meal for the first three hours. Volume samples will be collected by breathing into a metabolic chamber for 20 minutes.

1-Repetition Maximum Testing and Resistance Training Protocol:

1-repetition maximum testing will be completed on visit 1. Subjects will perform a 5-minute cycling warm-up, before completing a 1-repetition maximum on the leg press, leg extension, chest press, and lat pulldown. The multiple repetitions testing procedure will be utilized [10]. Subjects will perform an unloaded warm-up set of 10 repetitions, allowing for researchers to correct lifting technique if required. The following sets will be performed at progressively increasing loads until the participant reaches failure on that exercise. Repetitions will be considered valid if the participant can complete the entire repetition in a controlled, unassisted manner. Between sets, participants will be allotted a 2-minute resting period. The acute bout of resistance training will occur on visit 3. Subjects will perform a 5-minute cycling warm-up, followed by 4 sets of 10 repetitions of leg press, leg extension, chest press, and lat pulldown. The first set of each exercise will be performed at 65% of the participant's 1-repetition maximum. The following sets of each exercise will be performed at 80% of the participant's 1-repetition maximum until volitional fatigue occurs. For each set, strong verbal encouragement will be used. Participants will be allotted 2-minute rest periods between each set.

7 Potential Harms, Risks, or Discomforts

Body composition testing (DXA Scan): The radiation dose from one DXA scan is ~2 micro-Sieverts, which is about the amount of radiation an average person receives every 6 hours from natural radiation in our environment (i.e., from the sun, television and computer screens etc.). This procedure is painless and non-invasive.

Skeletal muscle biopsy procedure: The biopsy technique is routinely used in our research (>9500 biopsies in the last 20yr), and provided that proper precautions are taken, complications are rare. The muscle biopsy procedure will only be carried out by trained and experienced personnel who have been delegated to conduct the procedure. Participants can stop the procedure at any time if they wish. During the time that the sample is being taken (~5 sec), sensations of deep pressure in the thigh may be felt and, on some occasions, are considered moderately painful. However, the discomfort passes very quickly and participants are quite capable of performing exercise and daily activities afterwards. Once the anesthetic wears off, the leg may feel tight, and often there is the sensation of a deep bruise or "Charlie Horse." Analgesics such as Acetaminophen (Tylenol) or Ibuprofen (Advil) can be taken if the pain associated with the biopsy is experienced. It is also beneficial to periodically apply an ice pack to the biopsy site the following day, as this will help to reduce any swelling and any residual soreness. The following day, the leg may feel uncomfortable when going downstairs. The tightness or discomfort in the muscle usually disappears within 2 days, and subjects routinely begin exercising at normal capacity within a day.

There is a risk of internal bleeding at the site of the biopsy, which can result in bruising and temporary discoloration of the skin. There is also a risk of feeling lightheaded or faint as the procedure is occurring. On occasion, a small lump may form under the site of the

incision, but this normally disappears within 2-3 weeks. As with any incision, there is also a risk of infection; however, this risk is virtually eliminated through proper cleansing of the area and daily changing of wound coverings. To allow the incisions to heal and minimize any risk of infection, participants are instructed to clean the incision daily with 70% isopropyl alcohol wipes, as well as avoid submersing the incision in water. Showers are fine, but avoid baths, swimming, saunas, and jacuzis for at least 3-4 days following the biopsy procedure.

Heavy water (D2O): Heavy water contains deuterium, which is a hydrogen isotope, yet non-radioactive and is, in fact, already present in small amounts in the water we drink daily (i.e. 0.02%). In very large amounts, deuterium-labelled water can have adverse effects. A very high dose (more than 40 cups consumed in a very short time for a person weighing about 150 pounds) may cause a toxic response. In this study, participants will receive 30 times less than this amount. In previous research studies using heavy water, very few people who drank deuterium-labelled water reported temporary dizziness or vertigo. There is a 3.3% chance of encountering these side effects, and only upon the first- or second-time heavy water is ingested. If it does occur, the side effects may last up to two hours and will go away on their own. If this occurs, we ask that participants rest quietly and refrain from driving or operating heavy machinery. About half the water in the body is replaced every week. Once you stop drinking heavy water, deuterium will return to its normal concentration in 20-30 days.

Venous Blood Sampling: The insertion of a needle for blood sampling is a common medical practice and involves minimal risk, provided proper precautions are taken. The needle is inserted under sterile (alcohol will be used to minimize the chance of infection) conditions; however, there is a theoretical risk of infection. There is also a chance of bleeding if enough pressure is not put on the insertion site when the needle is removed. This may cause some minor discomfort and could result in bruising/skin discoloration that could last up to a few weeks. There is also a small risk that damage to the vessel wall could result in the formation of a small blood clot, which could travel through the bloodstream and become lodged in a smaller vessel. However, we have never experienced these types of problems in our laboratory after several thousand venous blood-sampling procedures.

Acute exercise: The potential risks and discomforts associated with the acute exercise bout are similar to those associated with any form of strenuous physical activity. These include fatigue, muscle strain, fainting, abnormal blood pressure, irregular heart rhythm, and in very rare instances, heart attack, stroke or death. We never had a serious incident while strength test in either younger or older adults in our laboratory.

7 Data Analysis Plan

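### Amino acid oxidation is read from breath ¹³CO₂ against one fasted baseline, while meal 1 carbohydrate differs threefold by arm and its ¹³C abundance is not controlled

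*Protocol*

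**What the plan says.** Section 4 of the protocol lists amino acid oxidation among the secondary endpoints. Section 3 (Procedure Overview) gives the method as "breath samples to assess amino acid oxidation". Section 6 (Breath Sampling) says the samples are stored "before the analysis of ¹³CO₂ enrichment by isotope ratio mass spectrometry". The ¹³C label comes from the leucine tracer named in Section 6 (Stable isotope-labelled amino acid infusion), alongside labelled phenylalanine and tyrosine. The tracer details are assigned to Figure 3, which is not shown.

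Section 3 (Feeding) fixes the infusion-day intake at "1.6g/kg of protein, 2.5g/kg of carbohydrate, and 0.5g/kg of fat", taken at once or in three equal meals. The beverage contains the protein blend "and maltodextrin to resemble a complete meal", and cookies supply the rest of the carbohydrate. Neither carbohydrate source is given a botanical origin or a ¹³C abundance.

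Under Visit 3, a baseline breath sample is taken after an overnight fast, before exercise and feeding. The split arm eats again at 1230h and 1700h. CO₂ volume is collected at baseline and hourly for three hours after meal 1. The Visit 4 breath sample is also fasted. No visit feeds the test meal without tracer.

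**The concern.** Breath ¹³CO₂ above baseline comes from two sources: oxidised leucine tracer, and a change in the natural ¹³C content of whatever else is being oxidised. After a carbohydrate meal, part of the exhaled CO₂ comes from that carbohydrate. If its ¹³C abundance differs from that of fasting breath, enrichment moves without any change in leucine oxidation. A fasted sample cannot capture this.

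Here the carbohydrate load is tied to the randomised regimen. It is threefold larger at meal 1 in the single-bolus arm, and it arrives later in the day in the split arm. Randomisation does not remove an artefact that belongs to the intervention. Equal daily totals do not remove it from comparisons at a given time.

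At stake is the reading of one secondary endpoint. Section 1 presents greater amino acid oxidation at higher doses as accepted background and favours a per-meal paradigm, so an arm difference in breath ¹³CO₂ is likely to be interpreted in that light, whatever its cause.

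**Working it through.** **Step 1: the threefold ratio.** The protocol's own per-meal figure is "three meals spread across the day, each with 0.53 g/kg protein". Check: 1.6/3 = 0.533, which agrees. The same division for carbohydrate gives 2.5/3 = 0.83 g/kg per split meal. The meal 1 ratio is 2.5/0.83 = 3.0, and the difference is 2.5 - 0.83 = 1.67 g/kg.

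**Step 2: shift in background.** None of the inputs in this step is in the documents; all are assumptions.
- Atom% ¹³C: A(δ) = 100r/(1 + r), with r = 0.0112372 × (1 + δ/1000).
- Fasting breath: δ = -26 or -22 per mil, so A = 1.0827 or 1.0871.
- Meal carbohydrate: enriched -11 (A = 1.0991), mixed -20 (1.0893), depleted -27 (1.0816).
- Share f of breath CO₂ from meal carbohydrate, single/split: 0.15/0.15, 0.25/0.20 or 0.45/0.15.
- Tracer signal S: 0.01 to 0.02 atom% excess.

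Between-arm shift = (f_single - f_split) × (A_carbohydrate - A_baseline), expressed as a percentage of S. With S = 0.01:

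| Carbohydrate | Baseline | A difference | 0.15/0.15 | 0.25/0.20 | 0.45/0.15 |
|---|---|---|---|---|---|
| Enriched | -26 | +0.0165 | 0% | +8% | +49% |
| Enriched | -22 | +0.0121 | 0% | +6% | +36% |
| Mixed | -26 | +0.0066 | 0% | +3% | +20% |
| Mixed | -22 | +0.0022 | 0% | +1% | +7% |
| Depleted | -26 | -0.0011 | 0% | -1% | -3% |
| Depleted | -22 | -0.0055 | 0% | -3% | -16% |

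For example, 0.30 × 0.0165 = 0.0049, and 0.0049/0.01 = 49%. With S = 0.02 every percentage halves.

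**Step 3: is S plausible?** Assume tracer at 6 µmol/kg/h, 20% oxidised, 80% recovered, and CO₂ output of 9 mmol/kg/h. Then S = 6 × 0.20 × 0.80/9000 = 0.0107 atom%. A source 15 per mil richer than breath adds about 15 × 0.00111 = 0.0167 atom% at full share. Each 10-point gap in share then adds 0.0017, or 16% of S, and 30 points add 47%. With 40% oxidised, S doubles and these become about 8% and 23%.

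**Step 4: is a gap in share plausible?** Glucose yields 6/180 = 33 mmol CO₂ per g, and a glucose polymer 6/162 = 37.
- For no gap: the split arm's 0.83 g/kg can yield 28 to 31 mmol/kg. At 9 mmol/kg/h that is 3.1 to 3.4 hours of total CO₂ output, so substrate need not run short early in either arm.
- For a gap: total CO₂ over three hours is 27 mmol/kg. A 10- to 30-point gap is 2.7 to 8.1 mmol/kg, or 2.7/37 = 0.07 to 8.1/33 = 0.25 g/kg more carbohydrate oxidised. That is 4% to 15% of the extra 1.67 g/kg.

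Neither zero nor 30 points can be excluded from the documents.

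**The case against.** The strongest reply is that the protocol is silent here rather than wrong. It gives no oxidation formula and does not say that background will go uncorrected; a laboratory procedure or an analysis plan not shown may deal with it. This stands in part. A reader might infer that the trial has decided to ignore diet background, and the documents do not show that. But ingredient choice and sample schedule are design matters. A later plan could model a post-meal background from ingredient data if someone measures the ingredients; it could not subtract one that was never sampled.

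A reader might also infer that the artefact inflates oxidation in the single-bolus arm and so favours the per-meal theory. The documents do not support this. It requires carbohydrate richer in ¹³C than fasting breath, and neither value is given. With a depleted source the shift reverses, and with a matched source it vanishes. Nor does a threefold load imply a threefold artefact, as Step 4 shows.

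Two further points stand. The contrast is one of timing, since daily carbohydrate is equal and breath is sampled to 2200. And the stated hypotheses concern MPS and sex, not oxidation.

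Replacing the leucine measure outright would be debatable. Unlabelled phenylalanine and tyrosine loads at meal 1 also differ threefold and disturb plasma steady state by arm, and the D₂O taken the day before could affect deuterium-based enrichments. Plasma hydroxylation is therefore better as a co-readout than as a substitute.

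**Conclusion.** The point holds as an uncontrolled, arm-linked background of unknown sign and size in one secondary endpoint. What the documents establish is the breath-based measure, the exact threefold difference in meal 1 carbohydrate, the fasted pre-meal baseline, the absence of any scheduled tracer-free fed sample, and the unstated carbohydrate source.

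The size, from about -16% through zero to about +50% of the tracer signal, rests wholly on assumed ¹³C abundances, shares of CO₂ and tracer signal; the tracer dose cannot be read from the available text. The range is illustrative and should not be quoted as an expected bias.

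The concern is greatest in the hours after meal 1, where the loads differ most and CO₂ volume is collected. Complete CO₂ volumes would not cure it, because it affects enrichment itself. The primary endpoint, MPS, is unaffected. This is a cheap improvement worth making before the first participant is fed, not a fault that undermines the trial.

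**What to change.** 1. In Section 3 (Feeding), require the maltodextrin and cookie carbohydrate to come from sources with ¹³C abundance close to fasting breath (not corn or cane), leaving macronutrient amounts unchanged.
2. Measure and record the ¹³C abundance of the meal ingredients, so that any residual background can be bounded and its sign known.
3. Report phenylalanine hydroxylation as a co-readout of oxidation, from the [D5]-Phe and labelled Tyr already infused and the plasma already drawn. Subtract the pre-infusion baseline, which also takes account of prior D₂O labelling, and use non-steady-state equations.
4. State that an arm difference in breath ¹³CO₂ alone will not be interpreted as a difference in amino acid oxidation.

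The cost is an ingredient constraint, an assay of the ingredients, and a little more analysis of plasma enrichments that are already a secondary endpoint. No visit or participant sample is added. The ingredient specification must be in place before feeding, because the ¹³C content of a meal already eaten cannot be changed.

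### CO2 volume is collected only at baseline and up to 3 h after the first meal, so breath-based amino acid oxidation at equal total protein depends on carrying early CO2 output forward

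*Protocol*

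**What the plan says.** Section 4 lists "Amino acid oxidation" last of four secondary endpoints. Section 3, Procedure Overview, names the means: "breath samples to assess amino acid oxidation".

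Section 6, Breath Sampling, sets two schedules:
- Enrichment: "Breath samples will be collected at the same time points of the blood draws". The listed draws run from 0500 to 2200 in both arms, with one more at +24 h.
- CO2 output: "volume will be collected at baseline and each hour after the first meal for the first three hours". The method is also given: "Volume samples will be collected by breathing into a metabolic chamber for 20 minutes". No other occasion for CO2 volume appears in the protocol.

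The arms, from the Trial Overview in section 3, are a "single bolus (one meal with 1.6 g/kg protein") and "three meals spread across the day, each with 0.53 g/kg protein". The Feeding text gives the same daily total to both arms (1.6 g/kg protein, 2.5 g/kg carbohydrate, 0.5 g/kg fat), taken at once or in three even doses. For the later meals, Visit 3 states: "Subsequent meals, if in the 3-meal group, will be consumed at 1230h and 1700h".

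**The concern.** Breath 13CO2 enrichment is a ratio. It becomes an oxidation rate only when multiplied by CO2 output. The protocol measures the ratio all day and the multiplier only early, at a time when the arms have not received the same amount of protein.

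The trial contrasts two ways of distributing the same daily intake. Section 1 cites increased oxidation after large doses as part of the background for a per-meal limit, so an oxidation result will be read as evidence on that question. If the only rates with measured CO2 output come from a window with a threefold dose difference, a higher value in the single arm is expected whether or not distribution over the day matters. A whole-day figure would avoid the unequal doses, but it would rest on CO2 outputs that nobody measured. This is a matter of data collection, and no later analysis plan can recover volumes that were not taken.

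**Working it through.** **Inputs.** The sampling times, CO2 volume schedule, doses and times of meals 2 and 3 come from sections 3 and 6. The clock time of the first meal is not given (it follows the exercise session). I assume 0630 to 0830; 0800 would match the 4.5 h between the later meals.

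**1. The protocol's own sampling counts.** Section 6 states 33 (split) and 28 (single) blood time points, which are also the breath time points.
- Split: 22 (0500–1530, half-hourly) + 8 (1630–2000, half-hourly) + 2 (2200 and +24 h) = 32.
- Single: 17 (0500–1300, half-hourly) + 9 (1400–2200, hourly) + 1 (+24 h) = 27.

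Each is one below the stated figure. Counting the venous sample at visit 1 would give 33 and 28, though the protocol does not say so. The difference does not affect this point.

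**2. What the rate needs.** Up to constants,

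oxidation rate ∝ (CO2 output × breath 13CO2 enrichment) / precursor enrichment.

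An error in CO2 output passes in full proportion into the rate. If the assumed output is wrong by a factor *a* in the single arm and *b* in the split arm, the ratio of the arms is wrong by *a/b*. It is unbiased only if *a* = *b*.

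**3. Protein eaten inside the CO2-volume window.**
- Daily totals: 1.6 g/kg in the single arm; 3 × 0.53 = 1.59 g/kg in the split arm. These agree to rounding.
- In the window: 1.6 against 0.53 g/kg; 1.6 / 0.53 = 3.02.
- Share of the daily total: 100% in the single arm; 0.53 / 1.6 = 33% in the split arm. The other 67% is eaten after the window closes.

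**4. How much of the day has a measured CO2 output.** There are four volumes per participant: baseline and three hourly values.

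| First meal (assumed) | Window ends | Gap to 1230 meal | 3 h as share of time to 2200 | Visit 3 breath samples after window: split / single |
|---|---|---|---|---|
| 0630 | 0930 | 3.0 h | 3/15.5 = 19% | 21 / 16 |
| 0700 | 1000 | 2.5 h | 3/15 = 20% | 20 / 15 |
| 0800 | 1100 | 1.5 h | 3/14 = 21% | 18 / 13 |
| 0830 | 1130 | 1.0 h | 3/13.5 = 22% | 17 / 12 |

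In the split arm, 15 listed enrichment samples fall after the 1230 meal and by 2200 (6 from 1300 to 1530, 8 from 1630 to 2000, 1 at 2200). Seven of them follow the 1700 meal. None has a concurrent CO2 volume.

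**5. Whether early output can stand in for later output.** In the window the single arm is handling a whole day's carbohydrate and fat (2.5 and 0.5 g/kg) and the split arm a third (2.5/3 = 0.83 and 0.5/3 = 0.17 g/kg). Afterwards the single arm has no further scheduled meal to 2200, while the split arm is fed twice more. There is thus no reason to expect *a* = *b*. The protocol has no figures from which either factor could be estimated.

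**The case against.** **The later meals are measured.** A reader might infer that oxidation after meals 2 and 3 goes unmeasured altogether. The documents do not support that. Visit 3 schedules breath samples every 30 minutes for 3 h after each later split meal, so enrichment is available there. What is missing is CO2 volume, and hence a rate based on measured output.

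**No section confines the comparison to 0–3 h.** A reader might infer that the trial will show more oxidation with the bolus and that the bias favours split feeding. That holds only if the analysis is limited to the early window, which the protocol does not say. With early output carried forward, the error is likely to differ by arm, but the document does not allow it to be sized. The rule for applying volume to later enrichment may also sit in an analysis plan or laboratory manual, so its absence from the protocol is not itself a fault. This objection stands against a firm claim of direction. It does not remove the problem, because any such rule would replace measurement by assumption.

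**The percentages are not a bias.** The share of clock time and the share of dose describe coverage. Neither estimates error in oxidation. This stands.

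**Reach is limited.** Oxidation is the last of four secondary endpoints, no hypothesis in section 5 concerns it, and the stated purpose is to compare muscle protein synthesis, which does not use CO2 volume. A reader might infer that the trial's main comparison is compromised; it is not.

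**Other data exist.** Labelled phenylalanine and tyrosine are infused and urine is collected, and these might inform oxidation by another route. The protocol ties oxidation only to breath, so this is a possibility and not a plan.

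**Conclusion.** The point holds as a limitation of one secondary endpoint. Oxidation rates based on measured CO2 output exist only at baseline and in the first 3 h after meal 1, when protein eaten differs 3.02 to 1. With the first meal assumed between 0630 and 0830, that window is 19% to 22% of the time from meal 1 to 2200.

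Two conditional conclusions follow. If the comparison is confined to 0–3 h, more oxidation in the single arm is expected from the dose imbalance alone. If it covers the day, it depends on carrying early CO2 output forward, an assumption that is doubtful and likely to fail differently by arm, by an amount that the protocol does not allow to be sized. Either way, the schedule does not support a comparison of the two regimens at equal total protein on measured data. It should be corrected before collection, since it cannot be repaired afterwards.

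**What to change.** Keep four 20-minute collections, but take them at baseline and once in each of the three post-meal windows (after meal 1, after 1230, after 1700), at the same clock times in both arms. Breath times common to both arms in the section 6 list are half-hourly from 0500 to 1300, then 1400, 1500, 1700, 1800, 1900, 2000 and 2200, so matching enrichment samples already exist. Define the endpoint as oxidation from the first meal to 2200, which leaves out the exercise bout, computed on those common times with CO2 output interpolated between collections.

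The cost is small: the same number of collections on the same visit. The downsides should be stated:
- Hourly resolution in the first 3 h is lost, which matters most for the single arm's main response.
- One volume per window still needs interpolation. The gain is that every meal time has a measured value in both arms.
- Follow-up remains unequal: 5 h after the last split meal, against 13.5 to 15.5 h after the single bolus under the assumed meal times.

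If the timing cannot move, report the 0–3 h result as a response to unequal protein doses, label any whole-day figure as resting on carried-forward CO2 output, and draw no bolus-versus-split conclusion on oxidation.
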